### 5.2 Pre-Study Evaluations (Baseline) (Within 21 Days Prior to the First Dose of ARQ 087)

After written informed consent is obtained, the subject's eligibility for the study and baseline disease state will be assessed.

The following will be evaluated and documented within 21 days prior to the first dose of ARQ 087 (Day -21 – Day 0):

- Obtain written informed consent from the subject or subject's legal representative
- Medical history (see Section 6.1)
- Physical examination, including mucous membranes and skin (see Section 6.2)
- ECOG PS (see Appendix 2)
- Vital signs (height, weight, temperature, blood pressure, respiration rate, and pulse)
- Fasting clinical blood tests (see Section 6.4)\*

- Urinalysis (see Section 6.4)
- Serum pregnancy test, if applicable (see Section 6.4)
- 12-lead electrocardiogram (ECG) (see Section 6.3)
- Echocardiography or Multiple Gated Acquisition (MUGA) scan, if applicable (see Section 6.3)
- Blood samples for tumor markers, if applicable (to be tested at study site)
- Collect archival and/or fresh tissue biopsy samples (see Section 6.8)
  - For subjects enrolled in the Expanded Cohort, archival samples should be collected for all enrolled subjects, paired biopsy is optional. Both archival and pre-treatment fresh tumor samples should be collected prior to the first dose of the study drug
  - For subjects enrolled in the Food-effect Cohort, both archival and paired biopsy should be collected. If archival tissue is not available, paired fresh tumor biopsy should be performed to confirm the subjects' FGFR1-3 or KIT/PDGFR status.
- Record prior and concomitant medications (medications used within 30 days prior to the first dose of ARQ 087)
- Tumor measurement and staging [e.g., computed tomography (CT) scan, magnetic resonance imaging (MRI) or positron emission tomography (PET)] (see Section 6.7, Appendix 6) **Note:** CT, PET, and MRI scans can be used as a Baseline assessment if they were performed within four weeks (28 days) prior to the first dose of ARQ 087.

\* Fasting clinical blood tests obtained during the Pre-study Visit can be used for Day 1 if they are performed within 72 hours prior to the first dose of the study drug (Cycle 1, Day 1 visit).

Subjects who satisfy all inclusion and exclusion criteria may be enrolled in the study.

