### 5.4.1 Cycle 1, Weekly Evaluations

#### 5.4.1.1 Week 1 (Day 1)

The following assessments will be made during this visit:

- Physical examination, including mucous membranes and skin
- ECOG PS
- Vital signs (weight, temperature, blood pressure, respiration rate and pulse)
- Fasting clinical blood tests (see Section 6.4)\*
- Urinalysis (see Section 6.4)
- Blood sample for pharmacokinetics (except Expanded Cohort, see Section 6.5)
- Blood samples for pharmacodynamics (see Section 6.6)
- Blood samples for tumor marker(s), if applicable (to be tested at the study site)
- 12-lead ECG (see Section 6.3)
- Record concomitant medications
- Dispense ARQ 087
- Assess AEs (after study drug administration)

\* Fasting clinical blood tests may be obtained within 24 hours of the visit.

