## 6.6 Pharmacodynamic Assessments

The goal of the proposed biomarker study is to evaluate the tumoral and serum- or plasma-based pharmacodynamic response in subjects treated with ARQ 087.

Information on tumor FGFR protein expression, gene copy number and mRNA amplification, and/or mutational/gene re-arrangement (fusion, translocation) status is required for this study. If these are not known, tumor biopsy should be done to assess these parameters prior to the first dose of ARQ 087. All baseline samples (archival or newly acquired) will be evaluated by immunohistochemistry (IHC), FISH (gene copy number), ISH or qNPA (mRNA amplification), and/or DNA sequencing (mutational/gene re-arrangement [fusion, translocation] status assessment).

Pathology specimens (pre- and post-treatment tumor biopsies) will be evaluated for changes in total FGFR1, total FGFR2, pFGFR, pFRS2 $\alpha$ , and/or pERK status by either IHC, mesoscale, or immunoprecipitation/Western blot analysis. A post-treatment tumor biopsy should be collected between Cycle 1 Day 22 and Cycle 2 Day 1 at least 1 hour post-dose. In subjects who have been on treatment  $\geq 8$  weeks and with the subject's agreement, additional post-treatment biopsies may be collected.

Blood samples (pre-dose) will be collected during Treatment Period 1 on Day 1, Day 2, Day 3, and Day 4 (Cohorts 1-4), and during Treatment Period 2 Cycle 1 (Cohort 5 and all subsequent Dose Escalation cohorts) on Day 1, Day 8, Day 15, and Day 22, and on Day 1 of Cycles 2-5 for evaluations of pharmacodynamic changes of factors including phosphate, glucose, FGF 19, 21, and/or 23 utilizing standard blood chemistry methodologies and ELISA-based assays.

For subjects enrolled in the Expanded Cohort, blood samples for evaluations of pharmacodynamic changes of FGF 19, 21, and 23 will be collected on Day 1 of the first six cycles.

Samples for pharmacokinetic and pharmacodynamic assessments will be labeled by personnel from the institution with subjects' study ID; subjects' identity will not be made known to employees from the Sponsor, additional collaborators, or other investigators. Samples will only be used for the purposes of the protocol and will only be used by ArQule's personnel or by an external laboratory chosen by ArQule to outsource the analyses according to internal guidelines. Samples will be kept until all protocol-related analyses are completed, for a period not exceeding 10 years or as required by local law.

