## 6.8 Tumor Biopsy

All enrolled subjects should agree to provide archival tissue and to have a fresh tumor biopsy.

- For ALL subjects, archival tissue biopsy samples should be collected
- For subjects enrolled into the Expanded Cohort, samples will be tested for genetic alterations, that may include FGFR genetic alterations, FGFR gene fusions, and KIT/PDGFR mutations
- For subjects enrolled in the Dose Escalation and Food-effect Cohorts, samples will be tested to assess protein expression levels of FGFR family members (FGFR1 and FGFR2) and/or to confirm the tumor's genomic profile, e.g., KIT/PDGFR mutation or *FGFR1-3* amplification, mutations/gene rearrangement (fusion, translocation) status
- If archival samples are not available, a fresh core needle biopsy or fine needle aspiration (FNA) may be collected during the Screening Period. Core needle biopsy samples collected within 30 days prior to the first dose of ARQ 087 are considered fresh.
- If allocated slots are available, for subjects eligible for enrollment in the Dose Escalation cohorts, paired (pre- and post-treatment) tumor biopsy is optional. The paired tumor biopsy will be done only if, in the Investigator's opinion, a minimally invasive biopsy may be performed.
- For all subjects enrolled in the Food-effect Cohort, a paired tumor biopsy is mandatory.
- In Cohorts 1-4, tumor samples will be collected at Baseline/archival and 4-6 hours after ARQ 087 administration on Day 1 of Treatment Period 1 or on Day 1 of Cycle 1 of Treatment Period 2. Starting with Cohort 5, a post-treatment tumor biopsy should be collected between Cycle 1 Day 22 and Cycle 2 Day 1 at least 1 hour post-dose. (Additionally, optional post-treatment biopsies may be collected at any time during treatment at least 1 hour post-dose.)
- For subjects enrolled in the Expanded Cohort pre- and post-treatment (paired) biopsy is optional. If a paired biopsy is deemed safe and with the subject's consent, the biopsy may be performed at Baseline, at any time point between Cycle 1 Day 22 and Cycle 2

Day 1 visits, and an additional optional biopsy may be performed at any time during the treatment including the End of Treatment Visit.

Prior to a subject's enrollment, the Investigator should establish availability of suitable pathology specimens and/or evaluate the subject's eligibility for tumor biopsy.

The testing may include assessment of FGFR1 and FGFR2 protein levels, pFGFR, pFRS2 $\alpha$ , and pERK expression levels.

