### 8.1.7 Further Adverse Event and Serious Adverse Event Defining

Wherever possible, a specific disease or syndrome rather than individual associated signs and symptoms should be identified. However, if an observed or reported sign or symptom is not considered a component of a specific disease or syndrome by the Investigator, it should be recorded as a separate AE.

Laboratory data are to be collected as stipulated in this protocol. Clinical syndromes associated with laboratory abnormalities are to be recorded as appropriate (e.g., diabetes mellitus instead of hyperglycemia).

Scheduled hospitalizations or elective surgical procedures will not be considered as AEs or SAEs.

Prolongation of a scheduled hospitalization can be considered an SAE.

Complications associated with scheduled procedures are considered AEs or SAEs.

Progression of disease is considered an efficacy outcome parameter and should not be captured as an AE or a SAE unless its outcome is death.

Adverse events including SAEs that occur following the execution of the ICF but prior to dosing will not be recorded as AEs or SAEs.

Adverse events including SAEs that occur after subjects receive any anticancer therapy other than the study-defined treatments will not be recorded as AEs or SAEs.

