## 8.2 Responsibilities and Procedures

The responsibility for the safety of an individual subject lies in all cases with the Investigator. This includes the timely review of all safety data obtained during the course of the study.

An Investigator must instruct his/her subjects to report any AE and SAE they experience.

Investigators capture, evaluate, and document all AEs and SAEs occurring during a subject's enrollment in the trial, commencing with the first day of treatment and including the protocol-defined 30-day post-treatment follow-up period (Code of Federal Regulations [CFR] 21 §312.64[b]) as source documents and on designated eCRF pages. These AEs/SAEs must be recorded in the EDC system of this study.

Investigators should assess AEs at each scheduled and non-scheduled visit, by the use of open-ended questioning, physical examination, and review of laboratory results.

Note: It is important to record all AEs and SAEs that result in temporary and permanent discontinuation of study drug, regardless of severity.

Investigators must report all SAEs, whether or not they are considered study-drug related, to the Sponsor or designee within 24 hours from knowledge of the event (see Section 8.4).

In cases of SUSARs, Investigators are responsible for reporting to their local IRBs/IECs; and the Sponsor or designee(s) is responsible for notifying regulatory authorities and all relevant Investigators of SUSARs.

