## 8.5 Post-Treatment Safety Follow-up

In this study, the post-treatment safety follow-up period is defined as 30 days after the last dose of assigned treatment. All AEs occurring during the study period from the time of the first dose of study drug administration to the last day of the 30-day post-treatment follow-up period will be captured.

All subjects will be followed for a minimum of 30 days after discontinuation of the study drug. All subjects should be instructed to reported AEs or SAEs occurring during the 30-day post-treatment safety follow-up period.

Unresolved study drug related (see Section 8.1.6 for definition) AEs and SAEs at the time of treatment discontinuation or new study drug related AEs and SAEs that occur during the 30-day safety follow-up period will be followed until they have, in opinion of the Investigator, resolved to baseline, have stabilized, or are deemed to be irreversible.

If a subject receives other anticancer therapy within the 30-day follow-up period, the follow-up for AEs will cease, beginning the first day of the new therapy.

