5.4.7 Analyses of Safety Variables

All analyses for the safety variables will be performed on safety population. Safety variables include adverse events, laboratory parameters, vital signs, ECOG performance status, 12-lead ECG and physical exams.

Descriptive statistics will be calculated for quantitative safety data, frequency counts and percentages will be compiled for classification of qualitative safety data. All percentages will be calculated based on the number of subjects in the safety population, unless otherwise indicated. Baseline is defined as the last non-missing value prior to the first dose date or on day 1, unless otherwise noted.

Adverse Events

Adverse events will be evaluated for severity using NCI-CTCAE, version 4.03. AE summaries will include treatment-emergent adverse events (TEAEs).

A TEAE is defined as:

- an AE which is not present prior to the first dose of ARQ 087 and started after taking the study drug during the treatment period or within 30 days after the last dose of the study drug;
- an AE which is present prior to the first dose of ARQ 087 and increased in severity after taking study drug during the treatment period or within 30 days after the last dose of study drug;
- an AE which is considered study drug-related regardless of the start date of the event.

All TEAEs will be coded using Medical Dictionary for Regulatory Activities (MedDRA[®]) Version 15.1 and summaries will be presented by system organ class and preferred term. Separate TEAE summaries will be generated for the following categories:

- All TEAEs
- Severe TEAEs (Grade 3 or higher)
- SAEs
- TEAEs related to study drug
- TEAEs leading to treatment discontinuation
- TEAEs leading to treatment interruption
- TEAEs leading to treatment interruption then dose reduction
- TEAEs resulting in death
- TEAEs listed according to maximum severity
- TEAEs classified as DLTs

TEAEs will be summarized by presenting the number and percentage of subjects having at least one TEAE in each system organ class and preferred term. A subject with multiple occurrences of the same TEAE will be counted only once in the AE category.

Separate TEAE summaries will be presented by system organ class, preferred term, and maximum CTCAE 4.03 grade. A subject with multiple CTCAE grades for the same TEAE will be summarized under the maximum CTCAE grade recorded for the event.

Laboratory Test

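### Adverse events between consent and first dose are barred from the record although some subjects must have a biopsy then, and the protocol's own SAE rules conflict on the point

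*Protocol*

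**What the plan says.** **Recording window.** Protocol 8.1.7: "Adverse events including SAEs that occur following the execution of the ICF but prior to dosing will not be recorded as AEs or SAEs". Section 8.2 has investigators capture events "commencing with the first day of treatment and including the protocol-defined 30-day post-treatment follow-up period", and 8.5 captures them "from the time of the first dose of study drug administration to the last day of the 30-day post-treatment follow-up period". The visit list for Cycle 1 Day 1 (5.4.1.1) places the AE assessment after dosing. None of the three schedules in Appendix 1 has an AE assessment at Baseline.

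**Procedures before dosing.** The baseline work-up takes up to 21 days (5.2). Section 6.8: "For all subjects enrolled in the Food-effect Cohort, a paired tumor biopsy is mandatory". Appendix 3 puts the first sample of that pair at Day -21 to 0. Where the required tumor FGFR information is not known, 6.6 says "tumor biopsy should be done to assess these parameters prior to the first dose of ARQ 087". A footnote to the Expanded Cohort schedule in Appendix 1 calls for a baseline biopsy if there is no archival tissue.

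**Text pointing the other way.** Section 8.1.7 also treats complications of scheduled procedures as AEs or SAEs and sets no time limit. Section 8.4 has each SAE of the investigation reported within 24 hours, related to drug or not, and gives no start point.

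**Analysis.** The second TEAE criterion in SAP 5.4.7 covers "an AE which is present prior to the first dose of ARQ 087 and increased in severity after taking study drug". The third admits any AE considered drug-related, whatever its start date.

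**The concern.** Safety and tolerability are the primary objective. A trial that calls for an invasive procedure should be able to report the harm that the procedure does. If a site follows the pre-dose exclusion, a serious bleed or infection after a study biopsy, but before the first capsule, leaves no AE or SAE record.

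The second worry concerns the TEAE tables. A worsening rule compares two severities. If the earlier one was never recorded, a symptom that the subject already had may be counted as new once it is noted after dosing, or a real worsening may be missed.

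**Working it through.** There is no rate, power or sample-size figure to reproduce. The check sets the rules side by side.

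**1. Who has a biopsy before dosing?**
- Food-effect Cohort: mandatory (6.8), at least six subjects. At the minimum of six, that is 6/120 = 5% to 6/60 = 10% of the 60 to 120 subjects planned. This is a share of subjects, not an event rate.
- FGFR status unknown: called for (6.6). Number not given.
- No archival tissue: permitted in 6.8, called for in the Expanded Cohort footnote. Number not given.
- Dose Escalation, paired biopsy: optional (6.8).
- Expanded Cohort, paired biopsy: optional in 3.1, 6.8 and its own Appendix 1 footnote, but mandatory in the footnote to the schedule for Cohorts 5-10. These passages must be reconciled.

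Not every pre-dose biopsy falls in the 21-day baseline period, because 6.8 accepts core samples taken within 30 days before first dose as fresh.

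**2. What should a site do with a serious biopsy complication after consent and before dosing?**
- 8.1.7, exclusion: do not record it.
- 8.2 and 8.5, capture periods: it falls outside both.
- 8.1.7, complications sentence: it is an SAE.
- 8.4: report it within 24 hours.

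The exclusion is the rule specific to this period, and both capture periods support it. The other two sentences are general and do not mention the period before dosing. A site can defend either course.

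**3. Would the analysis find it anyway?** The TEAE tables cover events after dosing, as they should. The Safety Population (SAP 4.2) requires some ARQ 087, so a subject harmed by the biopsy and never dosed is outside it. No other listing of procedural events is planned.

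**4. What can supply the pre-dose severity for the second TEAE criterion?**
- Laboratory tests: baseline values are collected, and SAP 5.4.7 plans shift tables of CTCAE grade. Worsening can be assessed.
- Conditions present before consent: outside the exclusion, and covered by medical history (6.1) and physical examination (6.2). No CTCAE grade is specified for them.
- Symptoms arising between consent and dosing: barred from the AE record by 8.1.7.
- Events judged drug-related: TEAEs under the third criterion, so no baseline is needed.

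What remains is non-laboratory signs and symptoms not judged drug-related. For these, neither document names a graded baseline. The SAP nevertheless expects some AE records with pre-dose onset: its example in 6.1.3 has an event dated January 2013 against a first dose on 1 February 2013.

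**The case against.** The best defense has four parts.

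- **The complications sentence in 8.1.7 and the rule in 8.4 already bring such SAEs in.** This stands in part. A reader might infer from the exclusion that no procedural SAE before dosing would ever be captured. The documents do not support that, since two passages point toward reporting. But those passages do not clearly override a more specific exclusion, so the conflict remains.
- **The baseline is not empty.** This stands. A reader might infer that the worsening rule has nothing to compare with. Medical history, examination and gradable laboratory values exist, and SAP 6.1.3 uses onset dates to keep pre-dose events out of the TEAE tables. Onset dates do not supply severity, however. The eCRF may ask for grades of ongoing conditions, but it is not among the documents.
- **The plainly mandatory group is small and in the past.** This also stands. Food-effect data had already been used to choose the Part 2 dose (Protocol 4.1.1), and SAP 2.2.1 describes Part 1 enrollment as past. The unknown-status and no-archival-tissue cases can still arise in Part 2.
- **An event before any dose cannot be a drug effect.** True. DLTs must be drug-related and fall in the first 28 days of continuous treatment (4.5), so events confined to the pre-dose period do not enter the MTD decision. That does not remove the need to record harm from study procedures.

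**Conclusion.** The concern holds in two limited parts.

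- The pre-dose exclusion in 8.1.7 contradicts a sentence of the same section and 8.4. As a result, a serious complication of a biopsy that the protocol calls for can go unrecorded.
- For non-laboratory symptoms, the second TEAE criterion has no specified graded baseline. The consequence is limited misclassification, which could go in either direction.

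The size of both is unknown. The documents give neither the number of pre-dose biopsies nor a complication rate, and the 5% to 10% above is only the share of planned subjects in the mandatory group at its minimum size. It would go too far to say that the primary safety results are distorted: the analysis is descriptive, and no direction or amount of error can be shown.

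This rests on two assumptions: that sites may follow the exclusion as written, and that the eCRF does not already collect graded baseline symptoms. If it does, the second part reduces to naming that record in the SAP. Overall this is a cheap improvement.

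**What to change.** 1. Reconcile Protocol 8.1.7, 8.2, 8.4 and 8.5 so that SAEs and AEs attributed to protocol-required procedures are recorded from consent.
2. In the SAP, list these events separately from TEAEs and without restriction to dosed subjects. The TEAE definition itself can stay as it is.
3. Record ongoing signs and symptoms with CTCAE grade before the first dose, and name that record in SAP 5.4.7 as the baseline for the worsening criterion.

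The cost is protocol and SAP wording and a few more entries per site, with no added subjects or visits. Whether existing eCRF pages suffice cannot be judged from the documents. The change is prospective, so it cannot recover events from pre-dose biopsies already done, including those in the Food-effect Cohort. The report should say so.

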#### Cohorts 1 – 4 (Part 1)

Given the long half-life (~ 1 week) of ARQ 087 in human subjects and hence the length of time (~35 days) to reach steady state, it was determined that it was reasonable to eliminate the single dose phase. Hence, starting with Cohort 5, treatment will consist of a single treatment period of continuous dosing that will cease at the subject's discontinuation from the study.

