### 7.7.2 Prohibited Treatment/Treatment to Be Avoided or Used with Caution

The following treatments are not allowed during the study:

- Any concurrent anti-cancer therapy including chemotherapy, radiotherapy, hormonal, targeted therapy, or immunotherapy
  - Palliative radiotherapy for local pain-control may be allowed, provided the subject does not meet criteria of progressive disease and treated lesions will not be included in the target/non-target lesion assessment
- Other investigational agents
- Immunosuppressive therapies, including systemic corticosteroids (except up to a 25 mg/day prednisone-equivalent dose or when used intermittently in an antiemetic regimen, for CNS metastases management or as premedication for imaging studies)

The following treatments should be avoided, if possible or used with caution during the study:

- ARQ 087 may inhibit CYP1A2 or CYP2D6 metabolism, hence co-administration of ARQ 087 with drugs known to be substrates of CYP1A2 or CYP2D6 should be avoided or used with caution (see Appendix 4)
- ARQ 087 may be a substrate and inhibitor of human P-glycoprotein (P-gp), therefore co-administration of ARQ 087 with drugs known to be P-gp substrates with narrow therapeutic index should be avoided or used with caution (see Appendix 5)
- Drugs with known liver toxicity, e.g., clotrimazole, should be avoided or used with caution; if such drugs need to be administered, LFT should be done every 4-5 days during the drugs' co-administration

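### Protocol 8.1.7 ends AE and SAE recording after other anticancer therapy without limiting this to the post-treatment period; with palliative radiotherapy permitted in 7.7.2, it contradicts 5.7, 8.2, 8.4 and 8.5

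*Protocol*

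**What the plan says.** Protocol 8.1.7, in the subsection on defining AEs and SAEs, closes with two exclusions. The first removes events between consent and dosing. The second is "Adverse events including SAEs that occur after subjects receive any anticancer therapy other than the study-defined treatments will not be recorded". Neither the protocol nor the SAP defines the study-defined treatments.

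Protocol 7.7.2 lists among treatments not allowed: "Any concurrent anti-cancer therapy including chemotherapy, radiotherapy, hormonal, targeted therapy, or immunotherapy". Directly under that bullet it makes an exception: "Palliative radiotherapy for local pain-control may be allowed, provided the subject does not meet criteria of progressive disease" and the treated lesions are left out of the lesion assessment.

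Other sections set a different recording window:

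- **8.2** has investigators document all AEs and SAEs from the first day of treatment through the 30-day follow-up, and adds: "Investigators must report all SAEs, whether or not they are considered study-drug related, to the Sponsor or designee within 24 hours" of learning of the event.
- **8.4** repeats the 24-hour duty for each SAE during the investigation.
- **8.5** captures all AEs from first dose to the end of the 30-day follow-up. Its only cut-off, which runs from the start of a new treatment, is "If a subject receives other anticancer therapy within the 30-day follow-up period, the follow-up for AEs will cease, beginning the first day of the new" (final word omitted). Section 5.7 has the same rule.

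In the SAP, the safety population (4.2) is everyone who received any ARQ 087. The TEAE window (5.4.7) is the treatment period plus 30 days, with no cut-off at other anticancer therapy.

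**The concern.** The 8.1.7 sentence is not tied to the end of dosing. A subject given permitted palliative radiotherapy during an ARQ 087 cycle has received an anticancer therapy in the protocol's own terms. A site applying 8.1.7 as written would then stop recording AEs and SAEs for someone still exposed to the drug.

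Safety and tolerability is the primary objective. An event that is never recorded leaves no missing-data flag; in the tables it looks the same as no event. Because the sentence sits in the section that defines AEs and SAEs, a site could also conclude that an excluded event is not an SAE for the 24-hour report. Sites that resolve the conflict differently would capture events inconsistently across the five to fifteen planned sites.

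**Working it through.** The plan gives no figure to reproduce. The check sets the sections side by side.

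**1. Does radiotherapy trigger the 8.1.7 sentence?** Section 7.7.2 names radiotherapy as an anti-cancer therapy, and the palliative allowance is an exception under that bullet. Whether permitted radiotherapy counts as a study-defined treatment is open. SAP 3.1.1 says the study drug is ARQ 087, but that is a different term in a different document. The trigger is therefore plausible on the text but not settled.

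**2. Can it happen during dosing?** Yes. The allowance applies only to subjects who do not meet progression criteria, so they lack the progression reason for stopping drug in 5.8. Leaving irradiated lesions out of the assessment presupposes that assessment continues.

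**3. What does each section require for an AE after permitted radiotherapy while still dosing?**

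| Section | Is the AE or SAE recorded? |
|---|---|
| Protocol 8.1.7, read literally | No |
| Protocol 8.2 | Yes, with all SAEs reported |
| Protocol 8.4 (SAEs) | Yes |
| Protocol 8.5 | Yes; the stop applies only within the 30-day follow-up |
| Protocol 5.7 | Its stop does not apply; it covers only the 30-day follow-up |
| Protocol Appendix 1 | AE assessment at on-treatment visits, with no exception |
| SAP 5.4.7 | Counted as a TEAE if recorded |

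On its literal reading, 8.1.7 cannot be reconciled with the others.

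**4. Effect on the analysis.** Let N be the number of treated subjects in a group, x the number who truly have a given TEAE, and m the number whose only occurrences fall in an unrecorded stretch. The reported incidence is (x − m)/N instead of x/N, a bias of −m/N. N does not shrink, because SAP 4.2 keeps every dosed subject. SAP 5.4.7 counts a subject once per TEAE, so someone who already had the event before radiotherapy does not add to m, although a later worsening would be missing from the maximum-grade table. In the Expanded Cohort of about 50–60 subjects, each unit of m lowers that event's incidence by 1/60 = 1.7 to 1/50 = 2.0 percentage points.

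**5. How large is m?** It cannot be derived. The documents give neither the frequency nor the timing of on-study radiotherapy, nor how sites would read 8.1.7.

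**The case against.** The strongest reply is that the operative sections already protect the data. Sections 8.2, 8.4 and 8.5 require full capture, Appendix 1 schedules AE assessment at on-treatment visits, and 5.7 and 8.5 confine the new-therapy stop to the 30-day follow-up. The 8.1.7 sentence directly follows the pre-dosing exclusion, so the pair can be read as the start and end of the AE window. Radiotherapy that the protocol itself permits could be read as study-defined, and the permission is conditional in any case. All of this stands. It makes the loss a risk rather than a certainty, but it does not remove the contradiction.

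Three stronger readings are tempting and are not supported:

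- A reader might infer that irradiated subjects drop out of the primary safety analysis. They do not. They stay in the safety population, their earlier events count, and scheduled laboratory, vital-sign, ECG and ECOG data continue. The protocol also states a primary safety objective, not a named endpoint.
- A reader might size the loss from a hypothetical subject irradiated early in a long course. The documents give no timing to support such a case, and a share of observation time lost is not a share of incidence lost.
- A reader might extend the point to the post-treatment stop, since 4.1.1 says "Given the long half-life (~ 1 week) of ARQ 087 in human subjects". But 5.7, 8.1.7 and 8.5 agree that recording stops once new therapy starts after treatment. That is a consistent design choice that avoids attributing another therapy's toxicity to ARQ 087.

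**Conclusion.** The point holds as an internal contradiction, and 8.1.7 is wrong as written. Its last sentence lacks the post-treatment limit found in 5.7 and 8.5 and, combined with 7.7.2, can be read to stop AE and SAE recording in subjects still taking ARQ 087. The direction of any bias is known: reported AE and SAE incidence can only be too low. The total size is not known. Any loss requires three things: that permitted radiotherapy is given during dosing, that a site treats it as outside the study-defined treatments, and that the site follows 8.1.7 over 8.2, 8.4 and 8.5. The documents do not show how often these coincide. The point still merits correction because it touches the primary objective and any loss would be invisible in the tables.

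**What to change.** - **Protocol 8.1.7:** limit the last sentence to new anticancer therapy started after the last dose of ARQ 087, matching 5.7 and 8.5.
- **Protocol 8.1.7 or 7.7.2:** state that palliative radiotherapy permitted under 7.7.2 does not end AE or SAE recording. This changes what is recorded, not which treatment is allowed.
- **SAP 5.4.7:** align the TEAE definition with the same post-treatment cut-off, so that the window ends at 30 days after the last dose or at the start of new anticancer therapy after the last dose, whichever is earlier.

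Continuing to record drug-related SAEs after new post-treatment therapy begins would be an optional addition, not the correction of an error.

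The cost is protocol and SAP wording, plus a few more AE and SAE entries per affected subject at visits already scheduled. Reported event rates may rise slightly. Protocol 7.7 already requires concomitant procedures on the eCRF, so the sponsor can list subjects irradiated while on drug and check whether their later events were recorded.
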